7 SAFETY MANAGEMENT

7.1 ADVERSE EVENTS

Client activity on the platform will be monitored daily by the online moderators and PSS. Signs of potential clinical deterioration will be reported to the client's treatment team. It is highly unlikely that clinical deterioration will be attributable to the Horyzons system. However, in the event that this becomes evident (e.g., a participant has clearly communicated that they have incorporated aspects of the Horyzons system into their delusional beliefs) the moderator will communicate this information to the clinical treatment team and/or the principal investigator. The principal investigator will inform the IRB of any concerns regarding adverse events associated with involvement in Horyzons.

7.2 SERIOUS ADVERSE EVENTS

Adverse events (AE) will be assessed to determine if they meet criteria for a serious adverse event (SAE). SAE, as defined by the FDA, will be systematically evaluated at each clinic visit. The trial period is defined from the time that the informed consent document is signed until 30 days after the last study visit. All SAE occurring during the trial period (including death due to any cause) or within 30 days after the last study visit will be communicated within 1 day of the investigator becoming aware of the event to designated personnel, using the telephone or fax numbers provided in the Study Reference Manual. Any fatal or life-threatening AE will be reported immediately, but no longer than 1 day from the time the investigator becomes aware of the event. A causality assessment will be provided for all SAEs. Critical follow-up information on SAEs will be provided as soon as it is available, but no longer than 1 day from the time the investigator became aware of the information. Other essential, but not critical, information may be reported within the following 5 days. An SAE, as defined by the FDA for use in clinical trials (<https://www.fda.gov/safety/medwatch/howtoreport/ucm053087.htm>), is an adverse event that satisfies any of the following criteria:

- Results in death.
- Is immediately life-threatening, including potentially life-threatening suicidal behavior or suicidal behavior that results in hospitalization.
- Requires inpatient hospitalization or prolongation of existing hospitalization.
- Results in persistent or significant disability or incapacity.
- Is a congenital abnormality or birth defect.
- Is an important medical event that may jeopardize the subject or may require medical intervention to prevent one of the outcomes listed above. Examples would include allergic bronchospasm that requires treatment in an emergency department, or a seizure that does not result in hospitalization.

The causality of SAEs (i.e., their degree of relatedness to study treatment) will be assessed by the investigators.

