4.1.2 BASELINE PROCEDURES

The study coordinator will meet virtually with client participants for approximately 45 minutes to complete all baseline measures. Informed consent and HIPAA authorization will be completed first via DocuSign's electronic consent platform, followed by a demographic and characteristic form collecting basic information about sex, age, ancestry, education (including parent education levels and zip code), cigarette/alcohol use, and basic history of medication/psychosis (including DUP). This will be followed by two psychological measures: the UCLA Loneliness Scale and MOS Social Supports Survey. Once the baseline study measures are complete, the study coordinator will guide clients through a 10-minute orientation to the Horyzons platform, including creating their personal profile and learning the features of the site. Client participants will be paid \$20.00 via Visa gift card for their time and completion of the visit.

The study coordinator will verbally highlight over the phone the study aims, what will be asked of the provider, the timeline of their participation, and that their participation is voluntary for each provider participant at the end of the screening. The provider participants will then be sent the consent forms via DocuSign to sign. In the email and at the top of the consent form in DocuSign there will be a number to call if they have questions. The language will explicitly indicate to call the number prior to consenting and signing the document if they have questions. The provider participants will then be sent the baseline surveys (demographics and CPCRN FQHC Survey) to complete on their own. Providers and PSS will be compensated \$30 for completing the consent and baseline measures.

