4.2 INTERVENTION PERIOD PROCEDURES

4.2.1 MID-TREATMENT PROCEDURES

Research staff will meet with client participants virtually to complete the measure battery (UCLA Loneliness Scale, MOS Social Support Survey and Feedback Survey) for the mid-treatment measures at approximately 6-month mark (+/- 4 weeks). Client participants will be compensated \$10 via Visa gift cards or Tango e-gift card for the approximate 30-minute visit. The study coordinator will send the electronic survey to the provider participants for the mid-treatment measures at the 6-month mark (+/- 4 weeks). Provider and/or PSS participants will complete electronic copies of the CPCRN Federally Qualified Health Centers Survey. Provider and/or PSS participants will be paid \$20.00 via Visa gift card or Tango e-gift card for these 40 minutes of their time.

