4.2.2 POST-TREATMENT PROCEDURES

Research staff will meet virtually with client participants to complete the finally set of aforementioned measure battery for the post-treatment visit at approximately 12-month timepoint (+/- 4 weeks). Client participants will be compensated \$10 via Visa gift cards or Tango e-gift card for the approximately 30-minute visit. There will be an additional follow-up survey 3-months post-intervention to complete the brief surveys. Clients will additionally be compensated \$10 for this completion of this visit. The study coordinator will send the electronic survey to the provider participants for the post-treatment measures at the 12-month mark (+/- 4 weeks). Provider and/or PSS participants

will complete electronic copies of the CPCRN Federally Qualified Health Centers Survey. After completing the electronic measure, the study coordinator will contact the provider participant to determine if they are willing to participate in the qualitative interview. If they are willing, the study coordinator will meet with them via videoconferencing and lead provider and PSS participants through a semi-structured qualitative interview regarding the Horyzons and various barriers and facilitators to its implementation within their clinic. Provider and PSS participants will be compensated \$20 for completing the post-treatment survey as well as an additional \$30/hr prorated to the nearest half hour if they complete the qualitative interview.

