4.3 Client Procedures

Upon completion of the 12-month intervention period, research staff will collect and amalgamate the passive engagement information of each participant on the platform to assess acceptability and feasibility of Horyzons as part of clinical care. Additionally, client participants' medical records will be examined for service use (e.g., emergency room visits, hospitalizations, outpatient care, etc.) as a result of their mental health.

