6.4 CONFIDENTIALITY OF DATA

Names and associated contact information for potential subjects during the recruitment phase will be stored in a manner similar to that used to store study data. This information will be kept in a locked file cabinet in a locked office in the Department of Psychology and Neuroscience at UNC or within the administrative or secure storage areas of the FEP clinics involved in this project. Contact information will be destroyed immediately after it is ascertained that an individual does not want to participate in the study. Declining participants' names will be retained on a secure password protected network to ensure that the same participant is not contacted more than once regarding participation.

A member of the research team will meet individually with the client in order to explain the components of the Horyzons platform, elicit and answer any questions the client may have, and obtain informed consent. We will also collect information about current suicidal ideation and stability (e.g., recent hospitalizations) to assess eligibility for participation. Persons will also be creating a Horyzons profile and answering questions about character strengths (e.g., curiosity, love of learning), which are embedded in the Horyzons platform. These data will be linked to other sources of information, including the record of their interactions within the Horyzons system (e.g., number of posts/comments on the community page).

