9 CONSENT PROCESS

Research staff will obtain informed consent directly from each subject. Staff obtaining the consent will provide the subject with a written document explaining the testing procedures and risks, and will answer any questions. We have several procedures in place to ensure that prospective participants fully understand the procedures, risks, and protections of the study. First, the consent form is written in easy-to-understand language. Second, the researcher reads the form to and with the potential subject and invites questions after each section of the form. Third, the researcher asks the subject a series of questions about the study, such as what they are to do if they no longer want to participate, or what they would do if they experience any stress during the protocol (this is to be used as comprehension check before consenting). As Horyzons is a fully virtual research study, participants will provide electronic consent via DocuSign's HIPAA compliant electronic consent platform.

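### SAE evaluation is tied to clinic visits, but the study's scheduled client contacts are virtual or survey-based, list no SAE question, and have no stated reporting route from the treating clinics

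*Combined protocol and SAP*

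**What the plan says.** Section 7.2 sets the rule: "SAE, as defined by the FDA, will be systematically evaluated at each clinic visit". It counts inpatient hospitalization and life-threatening suicidal behavior as SAEs, runs the trial period from consent to 30 days after the last study visit, and requires communication within 1 day of the investigator becoming aware.

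The procedures describe a different kind of contact. Section 9 begins a sentence with "As Horyzons is a fully virtual research study". Section 4.1.2 says: "The study coordinator will meet virtually with client participants for approximately 45 minutes to complete all baseline measures". Section 4.2.1 has staff meet clients virtually "to complete the measure battery (UCLA Loneliness Scale, MOS Social Support Survey and Feedback Survey) for the mid-treatment measures", at about 6 months (±4 weeks). Section 4.2.2 repeats that battery virtually at about 12 months (±4 weeks) and adds: "There will be an additional follow-up survey 3-months post-intervention to complete the brief surveys".

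Hospitalization appears in two other places. Section 6.4 says: "We will also collect information about current suicidal ideation and stability (e.g., recent hospitalizations) to assess eligibility for participation". Section 4.3, after a sentence on collecting engagement data once the 12-month intervention is complete, says that clients' "medical records will be examined for service use", with emergency visits and hospitalizations among the examples.

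**The concern.** The safety rule names an occasion that the schedule does not contain. The client contacts are itemized as consent, demographics, questionnaires, feedback and platform orientation, with no AE or SAE question or form. If the phrase instead means routine appointments at the FEP clinics, nobody is given the task of evaluating SAEs there or of passing them to the study. The information flows that are described run from study to clinic: clinical impressions are shared with the treating team (section 2.1, Treatment Period), and signs of deterioration are reported to it (section 7.1).

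The 1-day reporting limit does not close the gap, because it starts at awareness and so puts no bound on the time from event to detection. At stake are the completeness and timeliness of the SAE count, above all for hospitalizations.

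**Working it through.** The plan gives no figure to reproduce. The check compares the passages and does interval arithmetic on the visit windows.

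**1. Can 7.2 operate as written?** There are two readings.
- *Virtual study visits.* The synopsis (Study Phases) and sections 4.2.1 and 4.2.2 do use the word visit for some of these contacts, so 7.2 can be read as covering them. Sections 4.1.2 to 4.2.2 then fail to carry the rule out, since no SAE item is listed.
- *Routine clinic appointments.* No role, form or transmission route to the study is stated.

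**2. Longest gap if SAEs are evaluated at the virtual visits.** Inputs: 6 months = week 26 ± 4, that is weeks 22 to 30; 12 months = week 52 ± 4, that is weeks 48 to 56.
- Baseline to mid-treatment: 22 to 30 weeks.
- Mid- to post-treatment: shortest 48 − 30 = 18 weeks; longest 56 − 22 = 34 weeks.
- Mean delay at nominal times, with events spread evenly: 26 / 2 = 13 weeks.

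**3. Delay if a record review at week 52 were the only source.** With events spread evenly over 52 weeks, the mean is 52 / 2 = 26 weeks (about 6 months), range 0 to 52. An event at week 13 would wait 52 − 13 = 39 weeks. This needs three conditions together: no question at any visit, nothing found by the interim channels, and a single review after month 12. The last is an inference, because the record-review sentence in section 4.3 carries no date of its own.

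**4. Interim channels.**
- Daily moderation, with risk information screened twice daily (sections 6.1 and 7.1), works from platform activity.
- Outreach after two weeks without login, and a call after two more (sections 2.1 and 6.1), could shorten the delay to about 2 to 4 weeks for a client who stops logging in. An admission shorter than two weeks need not trigger it. The call is a general check-in with no SAE question specified. After it the account may be deactivated, and no further inactivity outreach is described.
- Weekly supervision calls and clinic-affiliated peer specialists on the study staff (section 2.1) are possible informal routes. No SAE-reporting duty is stated for them.

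**5. End of the window.** If the 12-month contact is the last visit: 12 + 1 = about month 13. If the 3-month follow-up is the last visit: 12 + 3 + 1 = about month 16. The synopsis calls the follow-up a visit; section 4.2.2 calls it a survey and then a visit. In either case the final 30 days have no scheduled contact. Section 7.3 adds a second endpoint for deaths, 30 days after the last day of the intervention.

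**6. How many events might be involved?** The documents give no hospitalization rate. Assuming an annual risk of 5% to 30%, and 40 clients (section 8) to 50 clients (synopsis, section 2.2), the expected number of clients hospitalized runs from 40 × 0.05 = 2 to 50 × 0.30 = 15. The chance of at least one is 1 − 0.95^40 = 0.87 at the low end.

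**The case against.** The strongest reply is that 7.2 speaks of the last study visit when it defines the trial period, and other sections call the virtual contacts visits. Read together, 7.2 already requires SAE evaluation at those contacts, and what remains is one ill-chosen word and an unlisted form. Section 7.2 also cites a Study Reference Manual that is not among the documents, and the form may be there. This reading is reasonable. It still leaves gaps of 30 to 34 weeks, no clinic-to-study notification, and procedure sections that do not show the evaluation. The manual is cited only for telephone and fax numbers.

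A reader might go further and infer that the study has no route to awareness at all, that detection lags six months on average, that disengaged clients are the least observed, and that nothing covers months 12 to 16. The documents do not support these claims:
- The interim channels exist, and screening looks beyond posts to blocked risk words, other users' reports and early warning signs.
- Clients who stop logging in are the group with active outreach, at least until deactivation.
- The six-month mean is a worst case that needs all the conditions in step 3.
- If the follow-up is a visit, 7.2 can be read as applying to it, so only the last 30 days lack a contact. If it is not, the window closes at about month 13.

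The study is also classed as non-significant risk, and entry excludes self-harm thoughts in the prior month and psychiatric hospitalization in the prior three months. That limits the severity of the point but does not remove it.

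**Conclusion.** The point holds as an inconsistency between 7.2 and the procedures, together with a missing notification route; it does not show that safety is unmonitored. On the literal reading, the rule has no scheduled study occasion on which to operate. On the favourable reading, SAEs are evaluated at virtual visits that may be 30 or 34 weeks apart, with a mean delay of 13 weeks under evenly spread events and nominal timing. Interim channels may reveal some events sooner, but none is described as SAE ascertainment, and short admissions and clients with deactivated accounts could be missed. The end of the window is uncertain by about three months (month 13 or 16). The conclusion assumes that no SAE form or clinic notification duty exists in material outside these documents. This is a cheap improvement.

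**What to change.** - In 7.2, replace the reference to clinic visits with the scheduled study contacts: 6 months, 12 months and the 3-month follow-up.
- Add a short scripted SAE question to those contacts and to the existing inactivity call.
- Run the planned record check at the same points and once more 30 days after the last contact, and state its timing in 4.3.
- Ask treating teams to notify the study of any hospitalization of an enrolled client. Visit questions alone leave gaps of up to 30 to 34 weeks, so this step matters most for timeliness.
- State whether the follow-up counts as a study visit, and reconcile the reporting windows in 7.2 and 7.3.

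The cost is protocol wording, a few minutes per contact, and brief extra record checks by existing staff. The change concerns how events are found and leaves clinical management as it is.

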7.3 DEATH

All deaths occurring within the trial period or within 30 days after the last day that the study intervention is administered will be reported within 1 day of the investigator becoming aware of the event. If an autopsy has been performed, results of the autopsy will be obtained and forwarded along with any available toxicology reports.

8 RECRUITMENT STRATEGY

Client study subjects will be drawn from the five first episode psychosis clinics in North Carolina (OASIS, Encompass, SHORE, Eagle, and AEGIS). The OASIS clinic was co-developed by [name] for the treatment of people with first episode schizophrenia. Currently, each clinic has a census of approximately 100-150 people and admits approximately 3-5 people per month. Approximately 40 client participants will be recruited from the five clinics, or around 6-8 client participants per clinic. Additionally, all providers have been self-identified as clinicians or PSS providing services to clients at one of the five participating clinics; therefore, we expect approximately 20 providers and/or PSS to participate in this project. As such, we expect that we will be able to recruit the number of participants we would like to involve in this project.

Once a client is referred to the study (or self refers), a study clinician or research assistant will speak with the individual (and any other individuals that she/he indicates, such as a family member) to describe the study protocol, expectations of study participation and potential study risks and benefits. If a client contacts a member of the research project to indicate interest in the study, a member of the research team will explain the study over the phone and use the screening questions to assess potential eligibility. Providers and PSSs will be contacted by phone and/or email in order to obtain consent and schedule focus groups.

Recruitment will be completed by the study coordinator, research assistant, and/or clinical providers involved in this project. The latter includes peer support specialists and providers at the local FEP clinics.

9 CONSENT PROCESS

Research staff will obtain informed consent directly from each subject. Staff obtaining the consent will provide the subject with a written document explaining the testing procedures and risks, and will answer any questions. We have several procedures in place to ensure that prospective participants fully understand the procedures, risks, and protections of the study. First, the consent form is written in easy-to-understand language. Second, the researcher reads the form to and with the potential subject and invites questions after each section of the form. Third, the researcher asks the subject a series of questions about the study, such as what they are to do if they no longer want to participate, or what they would do if they experience any stress during the protocol (this is to be used as comprehension check before consenting). As Horyzons is a fully virtual research study, participants will provide electronic consent via DocuSign's HIPAA compliant electronic consent platform.

